1. At estimated effective dose(s), and in the presence or absence of an estimated effective dose of a compatible adjuvant, is the vaccine safe and tolerated in nucleoside analogue (NA)-treated HBV patients with stable disease?
2. Is there evidence of induction of an immune response to the vaccine and what impact does an adjuvant (IC31®) have on the immune response – i.e. magnitude and anti-viral phenotype of T cell response.
3. To what extent is the immune response robust and durable?
4. Is there evidence of a pharmaco-dynamic effect of the vaccine indicative of potential efficacy i.e. reduction in serum HBsAg and/or increase in serum antibody to HBsAg; if so is the response dose dependent and is the response modified by inclusion of IC31®?

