4 TRIAL DESIGN

This is a double-blind, randomised, placebo-controlled, dose-ascending study to evaluate the safety, tolerability and immunogenicity of Vaccine FP-02.2 in HBeAg-negative hepatitis B patients as an add-on treatment to entecavir or tenofovir.

Actively treated subjects will receive either a Low or High dose of Vaccine FP-02.2 with or without IC31®.

A placebo arm is included in the study. Safety and immunogenicity data generated from the placebo arm will allow comparison to data generated from the Vaccine FP-02.2 High and Low dose study arms. The placebo group is also necessary to understand the rate of natural HBsAg seroconversion in an untreated study arm. An IC31® alone arm is included in the study which will additionally allow comparison of safety and immunogenicity data with data generated from the Vaccine FP-02.2 High and Low dose/IC31® study arms.

Approximately of 60 subjects (excluding replacements for subjects deemed ineligible after dosing) will complete this trial and will be assigned equally to 6 study arms (approximately 10/study arm).

Screening will occur up to 28 days prior to the first injection.

Up to 3 days before the first injection, eligible subjects will be randomised to treatment arm as shown in Table 2, depending on the cohort.

Subjects will receive 3 injections at intervals of 28 days (Day 1, Day 29, and Day 57). On the days of the injections the subjects will stay in the clinic for at least 4 hours after the first injection and 2 hours after the second and third injections and be monitored closely including an assessment of local reactions at the injection site. Approximately 24 hours after the first injection, the subjects will be asked to attend the clinic for safety assessments. For subsequent injections, subjects will receive a telephone call approximately 24 hours after each injection for safety follow-up. The subjects will be asked to return to the clinic 7 days after each injection for further assessments as well as 28 days after the last injection (Day 85). A follow-up visit will be performed 6 months after the end of the treatment period (i.e. 6 months after the last dose).

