7.6.2.2 Determination of virological parameters

- Quantitative HBV DNA levels (PCR)
- Quantitative HBsAg levels (ELISA)
- Quantitative HBsAb levels (ELISA)

Immunological (IFNy ELISpot assay) and virological assessments will follow the OECD Principles of GLP.

7.6.3 **Assessment schedule**

Screening Visit

The screening assessment is described in Section 7.2.1.

Randomisation will be performed by IRT up to 3 days prior to first injection to allow data from screening to be available for confirmation of eligibility criteria and for the central pharmacy to supply medication to site.

Visit 1:

The following assessments and procedures will be performed on Day 1:

Pre-vaccination

- Review of eligibility criteria
- Urine pregnancy test in women of childbearing potential
- Blood for CMI
- HBsAg and HBsAb monitoring
- Vital signs
- Physical examination
- Documentation of concomitant medication
- Documentation of AEs
- Vaccination
- Contact IRT for drug supply
- Dispense diary card

Post-vaccination

- Injection site tolerability

- Documentation of concomitant medication
- Documentation of AEs

The subject will be asked to stay in the clinic for at least 4 hours following the first injection.

Visit 2

The following assessments and procedures will be performed on Day 2:

- Vital signs
- Physical examination
- Injection site tolerability
- Documentation of AEs and concomitant medications
- Review diary card for local tolerability

Visit 3

The following assessments will be performed on Day 8:

- Vital signs
- Physical examination
- Injection site tolerability
- Safety laboratory tests
- Documentation of concomitant medication
- Blood for CMI
- Documentation of AEs
- Review diary card for local tolerability
- Dispense new diary cards

Visits 4 and 6 (administration of booster vaccinations)

The following assessments will be performed on Days 29 and 57:

Pre-vaccination

- Urine pregnancy test in women of childbearing potential (pre-vaccination)
- Safety laboratory tests (pre-vaccination)
- Vaccination
- Vital signs
- HBsAg and HBsAb monitoring
- Physical examination
- Documentation of concomitant medication
- Documentation of AEs
- Blood for CMI

Post-vaccination

- Injection site tolerability (post-vaccination)
- Documentation of concomitant medication
- Documentation of AEs
- Dispense diary card

The subject will be asked to stay in the clinic for 2 hours after each booster vaccination.

Telephone Contact 24 hours after booster vaccinations

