10.3 Statistical analysis plan

The proposed statistical analyses for this study will be detailed in a separate statistical analysis plan (SAP), which will be finalised prior to database lock. Any changes to the statistical analysis described in this protocol do not require a protocol amendment but must be described as a 'change to the protocol planned statistical analysis' in the SAP and the clinical study report.

The statistical analysis and report will conform to the relevant ICH requirements.

Data listings and summary tables will be generated using the software SAS® Version 9.3 or later. All data recorded in the eCRFs will be included in data listings. The SAS datasets and programs will be made available to the Sponsor at study closure.

Summary tables and data listings will be presented by treatment arm and time point.

The standard summary statistics for continuous variables will comprise number of valid observations, arithmetic mean, standard deviation, median, quartiles, minimum, and maximum. The geometric mean and coefficient of variation will also be presented for continuous variables which are positive and substantively positively skewed (such as liver enzyme levels, ELISpot counts and measures of viral load). The standard summary statistics for categorical data will comprise absolute and relative frequencies (proportions).

If continuous variables are assessed both at and after baseline, change from baseline will be calculated and summarised. If categorical variables are assessed both at and after baseline, then cross-tabulations will be presented by category at baseline.

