# 8.0 Study Time point Definitions

## 8.1 Baseline

Unless specified otherwise, baseline will be defined as the latest assessment taken prior to the first dose of investigational product.

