## 12.8 Virology Analysis

Blood samples will be collected for the assessment of virological parameters at the times indicated in **Table 1**.

Descriptive statistics for Virology parameters values:

- Quantitative Hepatitis B surface antigen (HBsAg) [presented in log10]
- Hepatitis B virus (HBV) DNA

and changes from baseline (in SI units) at each assessment time point will be presented by treatment group and visit for all subjects in the Immunogenicity Analysis Set and repeated for the Full Analysis Set if different.

Standard errors and 95% CIs derived from a one-sample t-test will be presented for change from baseline for HBsAg.

In addition, a line plot of the change from baseline in log10 HBsAg at each timepoint will be presented by treatment group.

The antibody to hepatitis B surface antigen (HBsAb) will be summarised by 'seroconverted' or 'not seroconverted' by visit for the Immunogenicity Analysis Set and repeated over the Full Analysis set if different. Seroconversion corresponds to HBsAb > 10 mIU/mL.

Individual subject results for all virology parameters will be listed for the Full Analysis Set.

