Table 14.2.2.2	Qualitative Virology Results by Time Point - HBsAb	Immunogenicity Analysis Set	
Table 14.2.2.3	Quantitative Virology Results by Time Point - HBsAg and HBV DNA	Full Analysis Set	X
Table 14.2.2.4	Qualitative Virology Results by Time Point - HBsAb	Full Analysis Set	
Figure 14.2.2.5	Line Plot of Change from Baseline in log10 HBsAg at each Timepoint by Treatment Group	Immunogenicity Analysis Set	
Figure 14.2.2.6	Line Plot of Change from Baseline in log10 HBsAg at each Timepoint by Treatment Group	Full Analysis Set	
Table 14.3.1.1	Summary of Investigational Product Exposure	Safety Analysis Set	
Table 14.3.2.1	Overall Summary of Adverse Events	Safety Analysis Set	
Table 14.3.2.2	Treatment-emergent Adverse Events by System Organ Class and Preferred Term	Safety Analysis Set	X
Table 14.3.2.3	Treatment-emergent Adverse Events by System Organ Class and Maximum Severity	Safety Analysis Set	
Table 14.3.2.4	Serious Adverse Events by System Organ Class and Preferred Term	Safety Analysis Set	
Table 14.3.2.5	Possibly Treatment-Related Treatment-emergent Adverse Events by System Organ Class and Preferred Term	Safety Analysis Set	
Table 14.3.2.6	Serious Possibly Treatment-Related Adverse Events by System Organ Class and Preferred Term	Safety Analysis Set	
Table 14.3.2.7	Possibly Treatment-Related Treatment-emergent Adverse Events by System Organ Class and Maximum Severity	Safety Analysis Set	
Table 14.3.2.8	Treatment-emergent Adverse Events leading to Discontinuation of Investigational Product by System Organ Class and Preferred Term	Safety Analysis Set	
Table 14.3.2.9	Adverse Events with Fatal Outcome by System Organ Class and Preferred Term	Safety Analysis Set	
Table 14.3.2.10	Adverse Events of Special Interest by System Organ Class and Preferred Term	Safety Analysis Set	
Table 14.3.3.1.1	Haematology Results by Time Point	Safety Analysis Set	
Table 14.3.3.1.2	Investigator Assessed Clinically Significant Postbaseline Haematology Results	Safety Analysis Set	
Table 14.3.3.1.3	Shift Summary of Haematology Results by Reference Range and Time Point	Safety Analysis Set	

Table 14.3.3.2.1	Biochemistry Results by Time Point	Safety Analysis Set	
Table 14.3.3.2.2	Investigator Assessed Clinically Significant Postbaseline Biochemistry Results	Safety Analysis Set	
Table 14.3.3.2.3	Shift Summary of Biochemistry Results by Reference Range and Time Point	Safety Analysis Set	X
Table 14.3.3.3.1	Quantitative Urinalysis Results by Time Point	Safety Analysis Set	

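### SAP 12.8 calls any HBsAb above 10 mIU/mL 'seroconverted' without reference to baseline, so the by-visit table reports prevalence under an incidence label

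*SAP*

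**What the plan says.** SAP 12.8 (Virology Analysis) says that HBsAb "will be summarised by 'seroconverted' or 'not seroconverted' by visit for the Immunogenicity Analysis Set", repeated for the Full Analysis Set if that differs. The rule is one sentence: "Seroconversion corresponds to HBsAb > 10 mIU/mL". The same section gives descriptive statistics and change from baseline to HBsAg and HBV DNA, but not to HBsAb. Subject-level results for all virology parameters are listed.

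For HBsAb, SAP Appendix 1 plans Tables 14.2.2.2 and 14.2.2.4, both titled "Qualitative Virology Results by Time Point - HBsAb", and the virology listing 16.2.6.2. No HBsAb shift table appears.

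SAP 8.1 supplies a general baseline: "baseline will be defined as the latest assessment taken prior to the first dose of investigational product". The flow chart samples HBsAb at screening and Days 1, 29, 57, 85 and 225, so a pre-dose value should exist for each subject.

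Protocol 10.3 sets the default for such variables: "If categorical variables are assessed both at and after baseline, then cross-tabulations will be presented by category at baseline". It sets a parallel default for continuous variables, namely that change from baseline is calculated and summarised. Protocol 7.6.2.2 lists HBsAb as a quantitative ELISA measurement, so both defaults apply to it. Protocol 10.3 lets the SAP alter the analysis without an amendment, provided that the SAP and the study report describe the change.

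On purpose, Protocol 4 (repeated in SAP 6.0) says: "The placebo group is also necessary to understand the rate of natural HBsAg seroconversion in an untreated study arm". Key issue 4 in Protocol 2 asks about "reduction in serum HBsAg and/or increase in serum antibody to HBsAg" as a sign of pharmacodynamic effect, and whether it depends on dose or on IC31.

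**The concern.** Seroconversion is a change of status between two times. The SAP defines it as a level at one time. The two agree only if nobody is above the threshold before dosing, and nothing in the plan secures that. Protocol 6.1 requires HBsAg positivity for at least 24 months, and neither 6.1 nor 6.2 refers to HBsAb.

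Two uses are affected. The first is the natural seroconversion rate that the placebo arm is meant to show, which is a rate of new events. The second is the question whether antibody rises. A yes/no status at each visit cannot show a rise in a subject who stays on one side of 10 mIU/mL. SAP 10.2 says the primary analysis will inform the design of the next study and the choice of formulation and dose, so these tables have a user.

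**Working it through.** The plan states no seroconversion rate, no expected baseline positivity and no power figure for this endpoint, so there is no figure of its own to reproduce. The check has two parts.

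**1. The rule set against the rest of the plan**

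- Threshold: HBsAb above 10 mIU/mL at the visit (SAP 12.8).
- Baseline-negative requirement: none in SAP 12.8.
- Exclusion of HBsAb-positive subjects: none in Protocol 6.1 or 6.2.
- Baseline value: available (SAP 8.1 and the flow chart), but not linked to the seroconversion rule.
- Cross-tabulation by baseline category: called for in Protocol 10.3, absent for HBsAb from SAP 12.8 and Appendix 1. Appendix 1 does name shift tables for haematology, biochemistry, urinalysis and ECG.
- Change from baseline in quantitative HBsAb: called for in Protocol 10.3, absent from SAP 12.8.
- Declared changes from protocol: SAP 4.1 lists two, on physical examination and on the Immunogenicity Analysis Set. Neither concerns HBsAb.

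**2. Size of the effect**

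Input: 10 subjects per arm, 60 in total (SAP 6.1). Let b be the number above 10 at baseline who stay above 10, and c the number of new converters by a given visit.

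- SAP rule: (b + c)/10
- Incident rate: c/(10 − b)

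| b | c | SAP rule at baseline | SAP rule at later visit | Incident rate |
|---|---|---|---|---|
| 0 | 0 | 0/10 = 0% | 0/10 = 0% | 0/10 = 0% |
| 1 | 0 | 1/10 = 10% | 1/10 = 10% | 0/9 = 0% |
| 1 | 1 | 1/10 = 10% | 2/10 = 20% | 1/9 = 11.1% |
| 2 | 1 | 2/10 = 20% | 3/10 = 30% | 1/8 = 12.5% |

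Each persistent baseline positive therefore adds 10 percentage points to its arm.

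How likely such a subject is depends on the baseline prevalence p, which the documents do not give. Over an assumed range, the chance of at least one among n subjects is 1 − (1 − p)^n:

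| Assumed p | Arm of 10 | All 60 |
|---|---|---|
| 0% | 0% | 0% |
| 2% | 1 − 0.98^10 = 18.3% | 70.2% |
| 5% | 1 − 0.95^10 = 40.1% | 95.4% |
| 10% | 1 − 0.90^10 = 65.1% | 99.8% |

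A Baseline row does not fully repair the table. Counts of 1/10 at baseline and 1/10 at Day 85 fit no change in anyone (incident 0/9). They fit equally well one subject falling to 10 or below while another rises above it (incident 1/9).

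**The case against.** The case on the other side is substantial, and part of it stands.

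- *The error would be visible.* SAP 8.4 puts a Baseline label in summary tables, and every virology result is listed by subject. With about 10 subjects per arm, a reader could find baseline positives and new crossings by hand. This stands. A reader might infer that the antibody question cannot be answered at all, or that pre-dose positives would pass unseen as vaccine responses. The documents do not support either inference. What is missing is a planned summary, not the data.
- *The count need not persist.* One might infer that a baseline positive is counted at every visit. That holds only while the value stays above 10.
- *Protocol 10.3 is a general default.* Protocol 10.10 leaves the detail of each virological endpoint to the SAP, the SAP nowhere says that the cross-tabulation is withdrawn, and table shells are not in the documents. The omission is therefore read from the text of 12.8 and the Appendix 1 titles. Even so, shift tables are named where they are planned, and Protocol 10.3 requires departures to be described.
- *The stakes are limited.* SAP 12.0 makes all endpoints exploratory and descriptive with no hypothesis tests, and HBsAb is not among the variables in SAP 7.1 or 7.2. No inference is invalidated. In a descriptive study, though, the tables are the result, so their labels should be right.
- *The blinded data review could catch it.* SAP 11.3 has that meeting review distributions and finalise the SAP. It could, but nothing directs it to this definition.
- *Terms differ.* Protocol 4 speaks of HBsAg seroconversion, whereas the SAP rule concerns antibody alone. That is true, but the antibody table is the only seroconversion summary planned.

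**Conclusion.** The point holds as a defect of definition and labelling. Followed as written, SAP 12.8 counts subjects who were above 10 mIU/mL before dosing as seroconverted. It therefore gives prevalence where the stated purpose of the placebo arm calls for a rate of new events. No planned summary gives the incident rate or the change in HBsAb, and the departure from Protocol 10.3 is not declared in SAP 4.1.

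The size is 10 percentage points per persistent baseline positive in an arm of 10. Whether it occurs depends on a prevalence that the documents do not state: at zero there is no effect, and at an assumed 2% to 10% the chance for a given arm is 18% to 65%. These figures give the chance that such a subject is present, not a bias in any comparison between arms. A reader might infer that the reported seroconversion rates will be wrong. The documents support only that they can be, and that the wording does not prevent it. Confidence is high on the wording and limited on the practical impact. It should be corrected before the SAP is finalised.

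**What to change.** 1. In SAP 12.8, define seroconversion as HBsAb at or below 10 mIU/mL at baseline (SAP 8.1) and above 10 mIU/mL at a post-baseline visit. Use baseline-negative subjects as the denominator and report baseline positives separately by arm.
2. Add a baseline-by-visit cross-tabulation of HBsAb category to Tables 14.2.2.2 and 14.2.2.4, and a descriptive summary of quantitative HBsAb and its change from baseline, as Protocol 10.3 provides. SAP 14.1 already sets a rule for values below the limit of quantification. If either summary is not wanted, declare its omission in SAP 4.1.
3. At minimum, if the by-visit table stays as it is, relabel the category 'HBsAb > 10 mIU/mL' so that it does not claim a change of status.

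Cost: a few lines of SAP text, one changed table layout (for both analysis sets) and, if adopted, one short descriptive summary. No new sampling is needed. The downside is a slightly smaller denominator in any arm with a baseline positive, for example 9 instead of 10.

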2 RATIONALE

Limited treatment options are available for CHB, the leading cause of end-stage liver disease and hepatocellular carcinoma worldwide. Only interferon-alpha has been able to induce HBsAg loss, which is considered to be a clinical “cure”, in a relatively low proportion of patients (<10%) and therefore establishing a clinical precedent for predicting efficacy. Interferons have a high cost, a poor tolerability (particularly in combination with ribavirin) and some HBV genotypes remain poorly responsive to treatment. Consequently, NUCs remain the main treatment strategies with five NUCs being approved in Europe to treat CHB. The most potent and preferred drugs, entecavir (brand name Baraclude®, Bristol-Myers Squibb) or tenofovir disoproxil furamate (tenofovir, brand name Viread®; Gilead), have a favourable side-effect profile and are able to induce HBV deoxyribonucleic acid (DNA) suppression in almost all patients and have a high barrier to resistance. However, these treatments suppress but do not eradicate HBV and rarely achieve clinical “cure” through HBsAg loss or seroconversion. Therefore, patients will require long durations if not life-long treatment to maintain virus suppression and to derive continued clinical benefit. Furthermore, the long-term safety of NUC therapy is currently unknown and costs for entecavir and tenofovir treatment are frequently reimbursed for only 2-3 years in many countries. Therefore, novel therapies that enable a timely stopping of NUC therapy are urgently needed.

Therapeutic vaccination is a very promising intervention for hepatitis B as a way to induce immune control over the disease. T cell responses have been shown to be critical for clearance of acute HBV infection. Cellular immune responses differ between the different phases of CHB and immune control of HBV can clearly be linked to the strength and quality of HBV-specific T cell responses ^{3, 2}.

Therapeutic HBV vaccines based exclusively on HBsAg have failed to show benefit due to pre-existing immune tolerance from high levels of circulating HBsAg, even under effective concomitant antiviral treatment. Novel vaccine strategies based on combinations of HBsAg with other HBV antigens have emerged¹ but have not yet shown efficacy in a clinical study. The limited clinical investigations to date have been completed to address T cell correlates of protection with limitations related to the genetic variability of the virus.

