6 ELIGIBILITY CRITERIA

6.1 Inclusion criteria

1. Male and female subjects aged 18-65 years.
2. Diagnosed with CHB defined as HBsAg positive for at least 24 months.
3. Subject has received entecavir or tenofovir for at least 2 years with a stable dose for at least 6 months prior to screening.
4. HBeAg negative for at least 2 years prior to inclusion in the study.
5. HBV DNA <50 IU/mL for \geq 12 months
6. ALT or AST \leq 1.5 x the ULN via the local laboratory at the Screening Visit
7. Able to give written informed consent to participate
8. Females should fulfil one of the following criteria:
 - a. At least one year menopausal
 - b. Surgically sterile
 - c. Same-sex relationship
 - d. Women of childbearing potential not surgically sterilised or with laboratory confirmed menopausal status are required to use a highly effective contraceptive measure with low used dependency such as:
 - o Combined (oestrogen- and progestogen-containing) hormonal contraception associated with inhibition of ovulation
 - o Progestogen-only hormonal contraception implants associated with inhibition of ovulation
 - o Intrauterine device (IUD)
 - o Intrauterine hormone-releasing system (IUS)
 - o Bilateral tubal occlusion
 - o Vasectomised partner – must have had medical assessment of successful surgery.

From screening until one menstrual cycle after the last dose of IMP (Day 57).

Subjects who practice true abstinence or who exclusively have same sex partners need not use contraception, provided it is in line with their preferred and usual lifestyle. Periodic abstinence (eg, calendar, ovulation, symptothermal, post-ovulation methods) and withdrawal are not acceptable methods of contraception. Should any such subject stop practicing true abstinence, they must use contraception as described above.

Males should fulfil one of the following criteria:

- Surgically sterile
- Willing to abstain from sexual intercourse or use a reliable form of contraception (e.g. condom with spermicide), if having sex with a pregnant or non-pregnant woman of childbearing potential, from screening until 3 months after the final dose of IMP.
- Surgically sterilised or post-menopausal female partner or same-sex relationship

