### 14.1 Immunogenicity

Any laboratory, immunogenicity or virology data that are below the limits of quantification will be imputed to one-half of the lower limit of quantification (LLOQ) for quantitative summaries and analyses.

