## Appendix 1 Tables, Figures, Listings, and Supportive SAS Output Appendices

List of Post-Text Tables, Figures, Listings, and Supportive SAS Output Appendices:			
Output	Title 1	Title 2	Top Line
Table 14.1.1.1	Disposition	All Screened Subjects	
Table 14.1.1.2	Important Protocol Deviations	Randomised Set	
Table 14.1.2.1	Demographic Characteristics	Safety Analysis Set	X
Table 14.1.2.2	Demographic Characteristics	Full Analysis Set	
Table 14.1.2.3	Demographic Characteristics	Immunogenicity Analysis Set	
Table 14.1.3	Medical History by System Organ Class and Preferred Term	Safety Analysis Set	
14.1.4.1	Concomitant Medications by WHO Drug Dictionary Preferred Term	Safety Analysis Set	
Table 14.1.4.2	Concomitant Medications that Began Before First Dose of Investigational Product	Safety Analysis Set	
Table 14.1.4.3	Concomitant Medications that Began on or After First Dose of Investigational Product	Safety Analysis Set	
Table 14.2.1.1	ELISPOT Score results by Peptide and Time point – Ex-vivo Assay	Immunogenicity Analysis Set	
Table 14.2.1.2	ELISPOT Score results by Peptide and Time point – Cultured Assay	Immunogenicity Analysis Set	
Table 14.2.1.3	ELISPOT Score results by Peptide and Time point – Ex-vivo Assay	Full Analysis Set	
Table 14.2.1.4	ELISPOT Score results by Peptide and Time point – Cultured Assay	Full Analysis Set	X
Table 14.2.1.5	Sum ELISPOT Score results by Time point – Ex-vivo Assay	Immunogenicity Analysis Set	
Table 14.2.1.6	Sum ELISPOT Score results by Time point – Cultured Assay	Immunogenicity Analysis Set	
Table 14.2.1.7	Sum ELISPOT Score results by Time point – Ex-vivo Assay	Full Analysis Set	
Table 14.2.1.8	Sum ELISPOT Score results by Time point – Cultured Assay	Full Analysis Set	X
Figure 14.2.1.9	Line Plot of Mean ( $\pm$ SE) ELISPOT Score against Time by Treatment Group and Peptide – Cultured Assay	Immunogenicity Analysis Set	
Figure 14.2.1.10	Line Plot of Mean ( $\pm$ SE) ELISPOT Score against Time by Treatment Group and Peptide – Cultured Assay	Full Analysis Set	

Figure 14.2.1.11	Line Plot of Individual Subjects' ELISPOT Score against Time by Treatment Group and Peptide – Cultured Assay	Immunogenicity Analysis Set	
Figure 14.2.1.12	Line Plot of Individual Subjects' ELISPOT Score against Time by Treatment Group and Peptide – Cultured Assay	Full Analysis Set	
Table 14.2.2.1	Quantitative Virology Results by Time Point - HBsAg and HBV DNA	Immunogenicity Analysis Set	

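### SAP 12.8 scores seroconversion on HBsAb alone and no planned table or figure counts HBsAg loss, so the natural HBsAg seroconversion rate that the placebo arm is meant to show is not a planned derived output

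*SAP*

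**What the plan says.** Protocol section 4 (Trial Design) gives one reason for having a placebo arm as follows: "The placebo group is also necessary to understand the rate of natural HBsAg seroconversion in an untreated study arm". SAP 6.0 repeats the sentence.

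Every subject enters antigen-positive. Inclusion criterion 2 in Protocol 6.1 reads "Diagnosed with CHB defined as HBsAg positive for at least 24 months". No eligibility criterion concerns HBsAb.

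SAP 12.8 then treats the two markers separately:

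- HBsAb is dichotomised by visit into seroconverted or not, with the rule "Seroconversion corresponds to HBsAb > 10 mIU/mL". The rule contains no HBsAg condition and no baseline condition.
- HBsAg is summarised only as a continuous variable: log10 values, change from baseline with a 95% CI, and a line plot of the change. Under SAP 14.1, values below quantification are replaced by half the LLOQ.

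Appendix 1 matches this. Tables 14.2.2.1 and 14.2.2.3 are titled "Quantitative Virology Results by Time Point - HBsAg and HBV DNA". Tables 14.2.2.2 and 14.2.2.4 are titled "Qualitative Virology Results by Time Point - HBsAb". Figures 14.2.2.5 and 14.2.2.6 plot log10 HBsAg change. Listing 16.2.6.2 gives the virology results by subject. SAP 4.1, which records changes from the protocol, does not mention dropping an HBsAg seroconversion rate.

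**The concern.** The word used for the placebo arm's purpose and the word used in the table appear to mean different things. The first concerns the surface antigen; the second is an antibody threshold that would be met whether or not the antigen persists.

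Two invented subjects show the effect. One has HBsAg 3000 IU/mL and HBsAb 12 mIU/mL: tabulated as seroconverted, with the antigen still there. The other has HBsAg below quantification and HBsAb 4 mIU/mL: tabulated as not seroconverted, and the antigen loss is counted nowhere. A third, already above 10 mIU/mL before dosing, would be scored as seroconverted from the outset.

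What is at stake is a stated purpose of the control arm and the meaning of a tabulated label. In a vaccine arm, a low-titre antibody rise with unchanged antigen would carry a word that the protocol associates with cure. In the placebo arm, such a subject would be read as natural seroconversion.

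**Working it through.** **1. What the documents mean by the term.** Neither document defines HBsAg seroconversion, so its meaning has to be inferred from use.

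- Protocol section 1 describes clinical cure as showing itself through loss of HBsAg.
- Protocol section 2 says "Only interferon-alpha has been able to induce HBsAg loss", calls that loss a cure, and names seroconversion beside antigen loss when saying that nucleos(t)ide treatment rarely achieves cure.
- Protocol section 1 reports that two large therapeutic-vaccine trials (references 8 and 15) found no HBsAg clearance. Protocol 2.1.2 reports anti-HBs antibodies in the reference 15 trial. On the protocol's own account, antibody can appear without antigen clearance.

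The reference 15 trial used a different vaccine in HBeAg-positive patients. It shows that the two markers can separate, not how often they would do so here.

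**2. Direction of the error.** If HBsAg seroconversion means antigen loss plus HBsAb > 10 mIU/mL at the same visit, everyone who meets it also meets the SAP rule. The SAP count therefore cannot be too low for that outcome. It is too high exactly when some HBsAg-positive subjects exceed 10 mIU/mL. Antigen loss without antibody is a separate outcome and has no count.

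**3. Possible size.** The plan states no rate to reproduce. Inputs:

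- Placebo arm: 5 (Cohort 1) + 5 (Cohort 2) = 10 subjects, from SAP Table 2.
- Whole trial: 10 placebo + 10 IC31 only + 4 × 10 vaccine = 60.
- q, the share of HBsAg-positive subjects with HBsAb > 10 mIU/mL: **not in the documents**. Assumed to be 1% to 10%, with subjects independent and true HBsAg seroconversion zero.

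P(at least one among 10) = 1 − (1 − q)^10. Expected number = n × q.

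| Assumed q | Expected of 10 placebo | P(at least one of 10) | Expected of 60 |
|---|---|---|---|
| 1% | 0.1 | 1 − 0.99^10 = 9.6% | 0.6 |
| 2% | 0.2 | 1 − 0.98^10 = 18.3% | 1.2 |
| 5% | 0.5 | 1 − 0.95^10 = 40.1% | 3.0 |
| 10% | 1.0 | 1 − 0.90^10 = 65.1% | 6.0 |

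One such placebo subject would be tabulated as 1/10 = 10%, with an exact (Clopper-Pearson) 95% CI of 0.3% to 44.5%, when the true count is zero.

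**4. What a corrected count could show.** For 0/10 the exact two-sided 95% upper limit is 1 − 0.025^(1/10) = 30.8%. The corrected rate would measure the right thing, but imprecisely.

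**The case against.** The strongest reply is that the term is undefined and the SAP analyses what the protocol asks. Question 4 in Protocol section 2 asks about a fall in HBsAg and/or a rise in antibody to it. Those are two separable readouts, and SAP 12.8 has one analysis for each. This has force: the documents do not settle the meaning, and the SAP may have intended antibody appearance only. But that reading fits poorly with the sentence about the placebo arm, which speaks of HBsAg seroconversion, and with sections 1, 2 and 2.1.2 of the protocol. If it was intended, the SAP should say so.

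Several other points stand and limit the concern:

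- A reader might infer that the rate can never be obtained. The documents do not support that. Listing 16.2.6.2 carries both markers, and with about 10 subjects per arm the joint status can be read by hand. A value set to half the LLOQ would also appear as the minimum in the HBsAg table, although that would not show how many subjects reached it.
- A reader might infer that the placebo rate will be overstated. That needs antigen-positive subjects above 10 mIU/mL, and the documents give no frequency.
- A reader might infer that the dose decision is at risk. Virology is part of the Day 85 primary analysis, but Protocol section 2 ties dose selection to T cell responses, neither HBsAb table is marked top line, and SAP 12.5 plans no efficacy analyses.
- The cut-off is stated openly and the table titles name HBsAb.
- Protocol 10.3 calls for cross-tabulation of categorical variables by baseline category, which would expose subjects already above the threshold. SAP 12.8 does not carry this over, and it would not bring in HBsAg.

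That the study is descriptive does not answer the point: a descriptive count should still measure what its label says.

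**Conclusion.** The concern holds in a limited form. SAP 12.8 scores seroconversion on HBsAb > 10 mIU/mL alone, even if HBsAg is still present and whatever the baseline HBsAb. No planned table or figure counts HBsAg loss, alone or with antibody gain. The rate that Protocol section 4 and SAP 6.0 give as a purpose of the placebo arm is therefore left to derivation by hand from listings.

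This conclusion rests on reading HBsAg seroconversion as including antigen loss, which the protocol's usage favours but does not define. Any numerical error is conditional. At an assumed 1% to 10% frequency of antigen-positive subjects above the threshold, the chance that the placebo arm contains at least one is 10% to 65%; at zero frequency the tabulated rate is not inflated. The missing count of antigen loss does not depend on that assumption.

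**What to change.** In SAP 12.8 and Tables 14.2.2.2 and 14.2.2.4:

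1. Relabel the present variable as HBsAb > 10 mIU/mL.
2. Add counts by arm and visit, with exact 95% CIs, of:
   - (a) HBsAg loss: HBsAg below a stated assay limit in a subject above that limit at baseline;
   - (b) HBsAg seroconversion: HBsAg loss plus HBsAb > 10 mIU/mL at the same visit, in a subject not above 10 mIU/mL at baseline.
3. State the assay limit. The documents give none, and they do not say that a value below quantification counts as loss.

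If only antibody appearance was meant by HBsAg seroconversion, say so in SAP 6.0 and 12.8. The relabelling is still needed.

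The cost is a short SAP edit, two extra table rows and their programming. The flow chart schedules HBsAg and HBsAb at the same visits, so no new sample is needed. The downside is a seroconversion rate that may be lower than the one now planned and will be imprecise.
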